7.4.1 Primary Efficacy Analyses

Separate primary analyses will be performed for each of the eight primary bone structure and bone remodeling biopsy endpoints listed in section 7.2.1. Since the study was terminated early and is thus under-powered, no corrections for multiplicity will be made in the analyses of the 8 primary efficacy endpoints. For each of these primary bone biopsy endpoints, the primary analysis will test for differences with respect to the time of the biopsy (baseline, 1, 2, and 4 year). These endpoints will be analyzed using repeated measures mixed models with the bone biopsy endpoint as the dependent variable, the baseline value of the bone biopsy endpoint and study cohort as covariates, biopsy time (baseline, 1 year, 2 year, and 4 year) as the repeated measure, and subject as the random variable. The repeated measures will include a time-dependent covariate to adjust the baseline biopsy of Cohort 2 for the time delay between the baseline biopsy and the start of hPTH treatment. This covariate will adjust Cohort 2 for any possible further progression of disease occurring between the baseline biopsy measures and the start of hPTH therapy. An indicator variable in the statistical model will set the effects of this time-dependent covariate to zero for Cohort 3 and for the post-baseline biopsies of Cohort 2.

Pairwise contrasts between the bone biopsy times will be performed within the repeated measures analyses to compare the effects of the biopsy times on the bone biopsy endpoints. Because the sample size for 2-year and 4-year biopsies are reduced in size due to withdrawal and the early termination of the study, the 2-, and 4-year biopsies may be combined into one group provided their effects are qualitatively similar (i.e. the estimates of their effects are in the same direction). If the 2- and 4-year biopsies are qualitatively different then the 4-year biopsies may be dropped from the analysis due to its small sample size. The post hoc pairwise comparisons among the

biopsy time-points will be corrected for multiple comparisons using Fisher's protected LSD with Bonferroni corrections when the overall effect of biopsy year is not statistically significant.

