7.4.2 Secondary Efficacy Analyses

7.4.2.1 Covariate adjustments for dose on the primary efficacy analysis models of the bone biopsy endpoints

The bone biopsy repeated measures analyses described in the primary analyses will be explored further by repeating the same analysis but with hPTH dose as an additional covariate. Four measures of dose will be tested as covariates: 1) average dose over the last 6 months prior to the bone biopsy or weaning whichever comes earlier; 2) average dose per kg body weight over the last 6 months prior to the bone biopsy or weaning whichever comes earlier; 3) total daily dose across the whole study up to the time of the bone biopsy or weaning whichever comes earlier; and, 4) total dose per kg of body weight across the whole study up to the time of the bone biopsy or weaning whichever comes earlier. The effects of these dose measures on the bone biopsy results will be modeled separately fitting both linear and quadratic (curvilinear) effects for the dose variable. The best covariate models will be selected based upon examination of the residuals and comparison of the Schwarz-Bayesian criterion.

The relationships between dose and bone biopsy endpoint will be graphically illustrated using scatterplots of the bone biopsy endpoint over dose with appropriate regression lines.

7.4.2.2 Sensitivity analyses of female menopause status in the primary bone biopsy efficacy models

Sensitivity analyses will be performed to test the effects menopause status in females on our best primary efficacy bone biopsy repeated measures models (with or without dose covariates, sections 7.4.1 and 7.4.2.1). Menopause status will be tested as a covariate in the statistical models (excluding males). The covariate for menopausal status will be parameterized into a categorical variable with 2 levels: 1) pre-menopausal female; and 2) menopausal or post-

menopausal female. If the data is rich enough, further exploratory analyses may test for interactions between dose, and menopausal status. Best models will be selected based upon residual analysis and the Schwarz-Bayesian criterion. Results will be summarized in tables.

7.4.2.3 Changes in bone mineralization density based on back-scattered electron imaging of bone-biopsies

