7.4.2.4 Repeated measures analyses of the non-biopsy secondary endpoints

The secondary non-biopsy secondary endpoints are listed in section 7.2.2.

Unlike the biopsy endpoints, the secondary non-biopsy secondary endpoints had measurements at baseline and then every 6 months over the 5 years of the study as compared to biopsies at baseline, 1, 2, and 4 years of hPTH treatment. As a complication, subjects were on hPTH therapy for various lengths of time due to study withdrawal and early study termination. Thus, the effects of study month are not the same for each subject with some subjects on hPTH therapy and some

subjects off hPTH therapy for the later study months. Thus, the 6-month time-points will be reduced to the following experimental time-points: baseline visit, 6-month study visit, end of hPTH therapy, and post-hPTH follow-up visit.

The effect of hPTH therapy over the experimental time-points (baseline, 6-month study visit, last hPTH treatment, and post-hPTH follow-up) on each of the non-biopsy endpoint parameters will be analyzed using repeated measures mixed models with the non-biopsy endpoint as the dependent variable, the baseline value of the non-biopsy endpoint, and study cohort as covariates, the experimental time-point as the repeated measure, and subject as the random factor. If dose is found to improve model fits in the bone-biopsy repeated measures analyses (section 7.4.2.1) then the effect of dose will be added as a covariate to these secondary repeated measures. Pairwise post hoc comparisons will be made to test for endpoints differences among the experimental time-points (baseline, 6-month study visit, last hPTH treatment, and post-hPTH follow-up). The significance of these post hoc pairwise comparisons will be corrected for multiple comparisons using Fisher's protected LSD. When the repeated measures overall effects of study time-point are not significant, Bonferroni corrections will be used to adjust the pairwise contrasts for multiplicity.

Residual analysis will be used to confirm that repeated measures model assumptions are reasonable. Log-transformations of the bone biopsy endpoints will be made if indicated by the residual analysis. The repeated measures will be fit using both a compound symmetry and an unstructured covariance structure. The better covariance structure will be selected as the model with the better Schwarz- Bayesian criterion.

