7.4.2.5 Summary of the effects of hPTH weaning on serum calcium, phosphorus, calcitriol, and biomarkers of bone turnover.

The effects of weaning subjects off hPTH will be summarized descriptively by the study PI.

Mixed models repeated measures analysis will test treatment effects on 10 outcome measures: serum calcium, serum phosphorus, 3 bone turnover markers (Osteocalcin, n-Telopeptide, and Alkaline Phosphatase), and 5 DEXA Bone Mass Density (BMD) parameters. The DEXA bone mass density measures included: AP spine BMD, femoral neck BMD, total hip BMD, Forearm BMD, and whole body BMD. Treatment effects will be summarized at three study time-points: Baseline (immediately at start of hPTH treatment), Treatment (immediately prior to Weaning, i.e. end of hPTH treatment), and Follow-up. The repeated measures analyses will be performed using each of these 10 outcome measures as the dependent variables, with random effects for subject,

and repeated fixed effects for 3 study time-points within a subject. These outcome measures will be log-transformed if necessary to normalize the data. Two covariance structures will be tested (compound symmetry and unstructured) and the covariance structure with the smallest Bayesian Information Criterion (BIC) and the best residual distributional properties will be used. Pairwise post hoc contrasts will be made to compare the effects of treatment at the study time-points. These post hoc pairwise contrasts will be corrected for multiple comparisons using Fisher's protected LSD with Bonferroni corrections when the overall effect of time is not significant.

Rho will provide figures with panel columns for the subject and the panel rows for the time course (baseline, during hPTH, through the start of weaning to the post-hPTH follow-up) of oral elemental calcium and calcitriol dosing, plasma calcium, and PTH dose.

7.4.2.6 Summary of hPTH therapy on nephrocalcinosis and nephrolithiasis by ultra sound and CT

The rate of new, stable, and progressing nephrocalcinosis and nephrolithiasis (NC/NL) in study subjects will be summarized.

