9. CHANGES TO THE ANALYSES PLANNED IN THE PROTOCOL

The study was discontinued early, due to pharmacy issues. Upon termination of new enrollment in June of 2015, subjects began to be slowly weaned off of hPTH. Of the 32 planned, newly enrolled subjects, only 19 were actually enrolled and treated and of these, 8 subjects provided their on-treatment biopsy. This early termination provides less power to detect significant differences in endpoints. We will evaluate the possibility of combining the 2- and 4- year biopsy groups to address this issue (see section 7.4.1 for details).

The primary bone biopsy endpoints have changed. The original primary endpoints included: 1) mineralized perimeter; 2) bone formation rate; 3) cortical width; 4) cortical area; 5) osteoid width; 6) osteoid perimeter; and 7) mineral apposition rate. These primary bone biopsy endpoints have been replaced with the eight primary endpoints listed in section 7.2.1. In the analysis of the pilot study of the first 5 patients as well as other relevant pilot studies, we learned that these are the more informative indices.

The primary and secondary analyses will be performed using repeated measures mixed models rather than the paired t-tests, ANOVA, and ANCOVA analyses as stated in the protocol.

Although the protocol specifies imputation analyses for all secondary endpoints collected every 6 months over the 5-year study period, for purposes of efficiency the sensitivity analyses using multiple imputation (Proc MI in SAS) of missing values will be initially limited to the primary efficacy bone biopsy endpoints. After reviewing patterns of missing-ness in the secondary endpoints, additional sensitivity analyses involving multiple imputations may be performed at the request of the PI.

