10. LIST OF PLANNED TABLES

Subject listings associated with the tables below will be provided. Experimental time refers to the baseline, last hPTH treatment, and post-hPTH follow-up visits. Additional tables (eg, those based on the results of sensitivity analysis) will be provided. Other displays, as requested by the PI may be provided as well.

Table Type	Table
Disposition	Summary of Subject Disposition
Demographics	Summary of Study Enrollment by Demographic Characteristics
hPTH Therapy	Summary of the Duration of hPTH Therapy
Primary Efficacy	Summary Statistics of Primary Bone Biopsy Endpoints by Biopsy Year. (Separate tables for Cohorts 2, 3, and Cohort 2 combined with Cohort 3)
	Repeated Measures Analysis of Primary Efficacy Analysis (Separate tables for Cohorts 2, 3, and Cohort 2 combined with Cohort 3)
Secondary Efficacy	Summary of Bone Mineralization Density Assessed by Back-Scattered Electron Imaging by Years of hPTH therapy
	Summary of Biochemical Markers of Bone Metabolism by Experimental Time Including the Statistical Significance of Changes.
	Summary of Blood and Urine Chemistries by Experimental Time Including the Statistical Significance of Changes.
	Summary of Bone Mineralization Density Assessed by DXA and Quantitative CT by Experimental Time Including the Statistical Significance of Changes.
	Summary of Nephrocalcinosis and Nephrolithiasis by Time on Study Drug
	Summary of Fatigue Symptom Inventory and 6-Minute Walk Test by Experimental Time Including the Statistical Significance of Changes.
	Summary of SF-36 Health Survey by Experimental Time Including the Statistical Significance of Changes.
Adverse Events (as provided to DSMB)	Summary of Adverse Events Occurring While on hPTH 1-34 or After Withdrawal from hPTH 1-34
	Summary of Adverse Events Occurring on or after hPTH 1-34
	Summary of Adverse Events Occurring While on Conventional Care
	Summary of Adverse Events for Subjects on Conventional Care
	Summary of Adverse Events Occurring While on hPTH 1-34 or After Withdrawal from hPTH 1-34: Current PI
	Summary of Adverse Events Occurring While on hPTH 1-34 or After Withdrawal from hPTH 1-34: Prior to Current PI
	Summary of Adverse Events Occurring While on Conventional Care: Current PI
	Summary of Adverse Events Occurring While on Conventional Care: Prior to Current PI

	Summary of Adverse Events Occurring While on hPTH 1-34 or After Withdrawal from hPTH 1-34; Related (Unlikely, Possible, Probable, or Definite) to hPTH 1-34

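### SAP 7.4.2.4 pools all durations of therapy into one end-of-hPTH level, so no non-biopsy model estimates the response at a fixed year on drug; its four levels also do not fit QCT

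*SAP*

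**What the plan says.** - **SAP 7.4.2.4** notes that subjects were on drug for differing lengths of time, so that later study months contain some subjects on hPTH and some off it. It concludes that "the 6-month time-points will be reduced to the following experimental time-points: baseline visit, 6-month study visit, end of hPTH therapy, and post-hPTH follow-up visit". The mixed model uses these four levels with baseline value and cohort as covariates, and tests all pairwise differences. Dose is added only conditionally: "If dose is found to improve model fits in the bone-biopsy repeated measures analyses".
- **SAP 7.4.2.5** (weaning analysis): "Treatment effects will be summarized at three study time-points". These are baseline, the value just before weaning, and follow-up.
- **SAP 10** (planned tables): "Experimental time refers to the baseline, last hPTH treatment, and post-hPTH follow-up visits". Month 6 is not in that list.
- **SAP 7.4.1** keeps calendar structure for biopsies, with "biopsy time (baseline, 1 year, 2 year, and 4 year) as the repeated measure". It allows years 2 and 4 to be combined, or year 4 to be dropped.
- **SAP 9**: of the new subjects, "only 19 were actually enrolled and treated and of these, 8 subjects provided their on-treatment biopsy". When enrollment ended in June 2015, "subjects began to be slowly weaned off of hPTH".
- **Protocol 2.2 and 10.1** aim at changes during the course of therapy and at a profile of each response over time that is analytical as well as graphical.
- **Protocol Appendix 24.4** schedules QCT at V0, V2, V4, V6, V8 and V10 only.

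**The concern.** The protocol introduction says it is unknown whether early skeletal changes last, cites data suggesting that turnover may normalise by two years, and names persistently raised markers as the worry. The biopsies can answer this only thinly, since 11 of 19 new subjects (58%) have no on-treatment biopsy. The six-monthly markers and DXA are the main remaining longitudinal data.

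In the planned model, a last value at month 12 and one at month 54 both count as end of therapy. If the response rises or falls after month 6, the end mean reflects the mix of stopping times as well as the drug. That mix was set partly by administration. From April 2010, when the current protocol was first approved, to June 2015 is 62 months, so time on drug at an administrative stop depends on date of entry. At stake are the reading of the end-of-hPTH estimates and any inferential statement about a given year.

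**Working it through.** The documents give no sample size or power for the non-biopsy endpoints, so there is no figure of the plan to reproduce.

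**1. What is tested.** Four levels give C(4,2) = 6 pairwise contrasts. One is between two on-drug levels (month 6 versus last value), and the second of these has no fixed time. Three levels in 7.4.2.5 give C(3,2) = 3 contrasts, none between two on-drug times. No level stands for year 1, 2, 3 or 4.

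**2. Does the end mean depend on stopping times?** End mean = Σ (share stopping at month t) × (change at month t). All values here are assumed:

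| Month | 6 | 12 | 24 | 36 | 48 | 60 |
|---|---|---|---|---|---|---|
| Sustained response | 10 | 20 | 20 | 20 | 20 | 20 |
| Peak, then return | 10 | 20 | 12 | 6 | 2 | 0 |
| Mostly short stops | 0.2 | 0.3 | 0.3 | 0.1 | 0.1 | 0 |
| Mostly long stops | 0 | 0.1 | 0.1 | 0.2 | 0.3 | 0.3 |

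- Peak and return, short: 2 + 6 + 3.6 + 0.6 + 0.2 = 12.4. Long: 2 + 1.2 + 1.2 + 0.6 + 0 = 5.0.
- Sustained, short: 0.2×10 + 0.8×20 = 18.0. Long: 20.0.
- Flat from month 6: the same value under any mix.

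**3. How much on-drug data the model uses.** A full-course subject has nine post-baseline on-drug visits (V1 to V9), and two enter: 7/9 = 78% unused (8/10 = 80% if V10 is on drug). Fewer are unused when subjects stop early. Three assumed stop patterns over months 6 to 60:
- even: one tenth at each of the ten visits;
- early: half at months 6 to 18, half at 24 to 60;
- late: 12.5% at months 6 to 18, 87.5% at 24 to 60.

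Mean on-drug visits are 5.5, 4.5 and 6.375. A subject uses two, or one if the last visit is month 6, so the mean used is 1.9, 1.833 and 1.958. Unused: 3.6/5.5 = 65%, 2.667/4.5 = 59%, 4.417/6.375 = 69%.

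**4. QCT.** V1 (month 6) and V11 have no scan, so QCT can fill only baseline and end of therapy if V10 is on drug. Five of the nine visits V1 to V9 (the odd-numbered ones) have no QCT, and the SAP does not say which scan then counts as the end value.

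**5. V10 (month 60).** Appendix 24.4 footnote 9 has subjects weaned and on standard care for at least 3 months by V10. The schedule rows agree, marking PTH therapy at V0 to V9 and conventional care at V10 and V11. Footnote 10 places V11 six months after stabilization starts: 66 − 6 = month 60. Protocol 4.6.1 likewise starts weaning after 5 years of therapy. Under footnote 9, stabilization starts by 60 − 3 = month 57, so V11 falls by month 63. With every tolerance at its limit, 60.5 − 2.5 + 6 + 0.5 = 64.5, still before 65.5, the earliest allowed date for a V11 at month 66. Both readings cannot hold. This affects only subjects who reach month 60.

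**6. What a time-on-drug model could deliver.** Take n from 19 (SAP 9) to 29 (adding at most the 10 earlier subjects in Protocol 10.3). Expected numbers at month 48 are n × 0.3 (even), n × 0.5 × 3/7 (early) and n × 0.875 × 3/7 (late): 5.7, 4.1 and 7.1 for n = 19; 8.7, 6.2 and 10.9 for n = 29. With an assumed correlation of 0.5 and compound symmetry, generalised least squares gives SEs against baseline of 0.19 to 0.29 SD at month 24 and 0.26 to 0.41 SD at month 48. For month 48 versus month 12, using only subjects present at both, SE = √(2(1 − 0.5)/m): about 0.49 SD for m = 4.1 and 0.30 SD for m = 10.9. The mixed model should do no worse.

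**The case against.** The SAP gives a sound reason for the reduction: after withdrawal and early termination, study month no longer means the same exposure for everyone. The reduction is stated and explained in 7.4.2.4, in a document that calls itself abbreviated. The protocol never promised a marker contrast at a named year, and late months are sparse. Total-dose covariates such as "total dose per kg of body weight across the whole study up to the time of the bone biopsy or weaning" grow with duration, and SAP 10 plans a table of duration on drug.

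Much of this stands. The reason is valid, and the four-point analysis should remain. It does not require pooling, however, because limiting the model to on-drug visits and indexing by months since first dose meets the same difficulty. The mitigations are partial: dose enters only if it helped the biopsy models, total dose mixes duration with dose level, and the duration table is not tied to the end estimates.

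A reader might infer that the time course on drug goes wholly untested. It does not: last value versus baseline, and month 6 versus last value, are both tested. A reader might also infer that about four-fifths of the on-drug data are discarded. That holds only for a full-course subject. Nor does the silence of SAP 9 show a hidden change, since the reduction is set out in 7.4.2.4.

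**Conclusion.** The point holds in a limited form. The end-of-hPTH level pools all durations without a time-on-drug term, and no model in 7.4.2.4 or 7.4.2.5 gives an estimate at a fixed year. Year by year, the course that Protocol 2.2 and 10.1 ask for is descriptive only. Even that rests mainly on the general summary rule in SAP 7.4, apart from the per-subject panels in 7.4.2.5 and the nephrocalcinosis table by time on drug.

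The size of the effect on the estimates cannot be derived from the documents. It is nil if the response is flat after month 6. The 12.4 versus 5.0 illustration rests on assumed responses and stopping mixes; it shows dependence and should not be read as a bias estimate for this trial.

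Three matters need no assumptions: the levels do not fit QCT, SAP 10 and 7.4.2.4 disagree on month 6, and the protocol contradicts itself on V10. As the endpoints are secondary, the priority lies between worth considering and should be done.

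**What to change.** - **(a) Supplementary model.** Keep the four-point analysis. Add, labelled supplementary, a mixed model for the continuous six-monthly endpoints on on-hPTH visits only, indexed by months since first dose. Use compound symmetry: baseline plus nine on-drug months would need 10×11/2 = 55 unstructured covariance parameters, against 2. Report estimates with 95% CI against baseline at months 12, 24, 36 and 48, and contrasts of months 24, 36 and 48 against month 12. The latter address persistence, which contrasts against baseline alone do not. Apply the multiplicity rule of 7.4.2.4, and describe only where fewer than 5 subjects remain.
- **(b) End level.** Report the distribution of time on hPTH beside each end estimate. State a rule that puts a last on-drug visit at month 6 into one level only.
- **(c) QCT and V10.** For QCT, use baseline and annual on-drug levels, without month 6 or V11. Reconcile footnotes 9 and 10, the treatment rows of Appendix 24.4 and Protocol 4.6.1 before classing any V10 value as on or off drug.
- **(d) Wording.** Align SAP 10 with 7.4.2.4 on month 6.

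The cost is SAP text and programming, with no new data. The SAP should state that late months are sparse (about 4 to 11 subjects at month 48 under the assumed patterns), contain only subjects still on drug, and rest on a missing-at-random assumption. In the smallest case (4.1 expected subjects), month 48 would be descriptive only.

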268 will have on biopsy results, randomization will also be stratified on status of prior study participation. The

269 subjects who were on HPTH therapy at the time of the protocol redesign are followed as a separate group
270 under this protocol.

271 **4.5 Study Procedures**

272 **4.5.1 Conventional Therapy Prior to Start of HPTH**

273 After the screening visit, newly enrolled subjects will complete a run-in period on conventional therapy of
274 calcium and calcitriol. The run-in period will last 2 to 6 months (\pm 1 month), depending on disease status
275 at enrollment and clinical response to optimized conventional therapy. During the run-in period, the
276 clinical investigators will provide conventional care for hypoparathyroidism, which includes periodic
277 blood and urine testing and adjustments in calcium and calcitriol dosing. If necessary, thyroid hormone
278 replacement will be optimized. Subjects may also receive vitamin D supplementation to ensure 25-OH-
279 Vitamin D levels \geq 25 ng/mL.

280 **4.5.2 Inpatient Baseline Visit and Start of HPTH Therapy**

281 This visit occurs at the end of the conventional therapy run-in period. The purpose of this 7 to 10 day
282 inpatient visit is to obtain baseline clinical and research measurements, to perform a baseline biopsy, to
283 initiate the 5-year HPTH therapy, and to randomize subjects to the timing of their second biopsy. This
284 visit is only required for newly enrolled subjects and subjects currently on conventional care under the
285 previous version of the protocol. Both groups of subjects will complete the same procedures at this visit,
286 except for the consent process and the iliac crest biopsy. Subjects on conventional care from the previous
287 version of the protocol will be re-consented at this visit after a review of their eligibility; however, they
288 will not undergo a biopsy at this visit. Their pre-conventional therapy biopsy will be substituted for their
289 baseline biopsy. The newly enrolled subjects will undergo a baseline iliac crest biopsy at this visit. At the
290 baseline visit, the following procedures will be conducted:

- 291 1. History
 - 292 a. Detailed history of current disease and adverse events
 - 293 b. Current medications
 - 294 c. Dietician consultation
 - 295 d. Short Calcium Questionnaire (Appendix 24.5)
 - 296 e. SF-36 Health Survey (Appendix 24.7)
- 297 2. Physical Exam

- 298 a. Height and weight measurement

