- 338 8. Randomization of newly enrolled subjects and previously enrolled conventional care subjects to
339 a second biopsy after 1, 2, or 4 years of HPTH therapy. A dynamic allocation scheme will be
340 used to ensure balance across biopsy arms by gender, menopausal status, and prior participation
341 in the protocol (see Section 10.3). The principal investigator or designee will perform the
342 randomization procedure using a secure, web-based randomization system.

343 All subjects will receive HPTH at a starting dose of 0.2 µg/kg/dose subcutaneously twice a day. After the
344 initial dosing, HPTH will be titrated based on serum calcium levels, according to the dosing algorithm in
345 Appendix 24.10. Each subject will receive education and written materials about HPTH administration
346 and dosing adjustment prior to discharge (Appendix 24.11). The drug will be provided to all subjects free
347 of charge. The NIH Clinical Center Pharmaceutical Development Service (PDS) will be responsible for
348 labeling, storing, preparing, dispensing, and maintaining accountability records for HPTH.

349 **4.5.3 Follow-up Visits During HPTH Therapy**

350 Subjects will be seen at the NIH every 6 months (± 2 weeks) until they have completed up to 5 years of
351 HPTH therapy. The second biopsy will occur at one of these visits, with the timing of that biopsy
352 determined by random assignment. Subjects currently on HPTH therapy under the previous version of the
353 protocol will be re-consented at the first follow-up visit they attend. Follow-up visits may be conducted
354 on an inpatient or outpatient basis at the discretion of the investigator, except for biopsy visits which must
355 be inpatient. Follow-up visits will last 1-3 days if a biopsy is not being performed and 5-7 days if a biopsy
356 is being performed. Additional visits may be scheduled at the discretion of the investigator in order to

357 assess adverse events or other problems that may arise. All subjects will undergo the procedures and tests
358 described below at each follow-up visit, unless otherwise noted:

359 1. History

360 a. Detailed history of current disease and adverse events

361 b. Current medications

362 c. Dietician consultation

363 d. Short Calcium Questionnaire (Appendix 24.5)

364 e. SF-36 Health Survey (Appendix 24.7).

365 2. Fitness measures

366 a. Fatigue Symptom Inventory (Appendix 24.8)

367 b. 6-Minute Walk Test (Appendix 24.9)

368 3. Physical Exam

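### SAP 7.4.2.4 may put hPTH dose, with no coding defined, into the models whose time contrasts are the hPTH effect, and keeps no dose-free analysis for seven outcomes or any 6-month contrast

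*SAP*

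**What the plan says.** SAP 7.4.2.4 reduces the six-monthly visits to four time-points: baseline, 6 months, end of hPTH therapy and post-hPTH follow-up. It describes what the models estimate as "The effect of hPTH therapy over the experimental time-points". If dose is found to improve fit in the biopsy models of 7.4.2.1, "then the effect of dose will be added as a covariate to these secondary repeated measures". The pairwise comparisons among time-points come next, with no other model named as their source.

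The only dose definitions are the four in 7.4.2.1. The first is "average dose over the last 6 months prior to the bone biopsy or weaning whichever comes earlier"; the other three also end at the biopsy or weaning. For the biopsy endpoints, 7.4.2.1 repeats the 7.4.1 analysis with dose added, so the dose-free version survives there.

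SAP 7.4.2.5 has separate models with no dose term: "Mixed models repeated measures analysis will test treatment effects on 10 outcome measures". These use three time-points and omit the 6-month visit. SAP section 10 plans inferential tables for endpoints that 7.4.2.5 does not cover, for example "Summary of SF-36 Health Survey by Experimental Time Including the Statistical Significance of Changes".

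On dosing, Protocol 4.5.2 sets the baseline visit to "obtain baseline clinical and research measurements, to perform a baseline biopsy" and to start HPTH. It then states that "HPTH will be titrated based on serum calcium levels".

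**The concern.** Protocol 10.3 confirms that there is one treatment group, so the change from baseline is the only estimate of what hPTH does to these endpoints. Dose is zero before the drug starts and positive afterwards. If dose enters by visit, the adjusted contrast between an on-treatment visit and baseline compares the two at equal dose, which is not the effect of hPTH. Dose is also a post-baseline variable titrated on serum calcium, itself one of the endpoints.

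SAP 7.4.2.4 does not say which of the four measures to use, whether the term is linear or quadratic, what value applies at baseline, 6 months or follow-up, or whether dose is centred. Those choices decide what the contrast means. Where 7.4.2.4 and 7.4.2.5 cover the same outcome, the SAP does not say which estimate is reported. At stake is whether a real change is reported as absent, inflated or much less precise because of a coding decision left until after the data are seen.

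**Working it through.** **1. Which results have no dose-free model**

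The plan's count in 7.4.2.5 reproduces: serum calcium 1 + serum phosphorus 1 + turnover markers 3 + DXA sites 5 = 10.

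The modelled non-biopsy outcomes in 7.2.2.3, counting each questionnaire once and leaving out nephrocalcinosis and nephrolithiasis (only summarised, 7.4.2.6), are: turnover markers 3 + serum calcium 1 + urine calcium 1 + 1,25-OH2-vitamin D 1 + DXA sites 6 + quantitative CT 1 + Fatigue Symptom Inventory 1 + 6-minute walk 1 + SF-36 1 = 16.

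Serum phosphorus is not on that list, so 7.4.2.5 covers 10 − 1 = 9 of the 16. The remaining 16 − 9 = 7 are urine calcium, 1,25-OH2-vitamin D, quantitative CT, lateral spine DXA, Fatigue Symptom Inventory, 6-minute walk and SF-36. The count becomes eight if the alkaline phosphatase in 7.4.2.5 is not the bone-specific marker. No 7.4.2.5 model has a 6-month time-point, so every 6-month contrast rests on 7.4.2.4.

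**2. What the adjusted contrast estimates**

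With a subject effect, time effects and visit-level dose with slope b:

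adjusted change = total change − b × (mean dose at end of therapy − mean dose at baseline).

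Scale the mean on-treatment dose to 1 and the true change to 1.0. The adjusted change is then 1 − b × (1 − 0) = 1 − b.

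- Effect proportional to dose: b = 1, adjusted change 0.
- On/off effect unrelated to dose: b = 0, adjusted change 1.
- Poor responders titrated up, taken as effect = 1 − 0.5 × (dose − 1): b = −0.5, adjusted change 1.5.

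If the pre-weaning dose is carried to follow-up, a subject's dose pattern is (0, 1, 1, 1) while the proportional effect pattern is (0, 1, 1, 0). Deviations from the subject mean are (−0.75, 0.25, 0.25, 0.25) and (−0.5, 0.5, 0.5, −0.5). The slope is (0.375 + 0.125 + 0.125 − 0.125) / (0.5625 + 3 × 0.0625) = 0.5 / 0.75 = 2/3, so the adjusted change is about 0.33. In the titration case it is 1 + 0.5 × 2/3 = 1.33.

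**3. Simulation of end of therapy minus baseline**

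Inputs: 19 subjects (new subjects treated, SAP section 9; the cohort 2 number is not given) and four time-points. Assumed, because the documents give none: dose CV 0.3 and 0.5, 15% variation between the two on-treatment doses, between-subject SD 0.7, residual SD 0.7. Within-subject least squares, 4,000 replicates. Entries are mean (SD of the estimate).

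| Dose CV, effect shape | No dose | Dose 0 off drug | Pre-weaning dose carried forward | Centred within time-point |
|---|---|---|---|---|
| 0.3, proportional | 0.99 (0.23) | −0.01 (0.58) | 0.37 (0.62) | 0.99 (0.23) |
| 0.3, on/off | 1.00 (0.22) | 0.99 (0.57) | 0.99 (0.61) | 1.00 (0.22) |
| 0.3, titrated | 1.00 (0.23) | 1.50 (0.58) | 1.31 (0.62) | 1.00 (0.23) |
| 0.5, proportional | 1.01 (0.26) | −0.01 (0.41) | 0.35 (0.45) | 1.01 (0.26) |
| 0.5, on/off | 0.99 (0.23) | 0.99 (0.42) | 0.99 (0.44) | 0.99 (0.23) |
| 0.5, titrated | 0.99 (0.23) | 1.50 (0.41) | 1.31 (0.45) | 0.99 (0.23) |

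Centring on the overall mean gives the same results as dose 0 off drug. For the on/off effect with dose 0 off drug, the standard error grows by 0.57/0.22 = 2.6 and 0.42/0.23 = 1.8.

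Compound-symmetry mixed models with 20 subjects and dose CV 0.2 to 0.5 show the same pattern:

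- Proportional effect: about 0.0 to 0.2 with dose 0 off drug, and 0.3 to 0.4 with dose carried forward. With dose 0 off drug, significance falls from 100% without dose to 3–6%.
- On/off effect: 1.0, with the standard error multiplied by 1.7 to 3.6.
- Titration: mostly 1.3 to 1.8, and up to 3.2 under strong titration.
- Dose carried forward: follow-up versus end of therapy stays at −1.0.
- One dose value per subject: no contrast changes.

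**4. How readily the rule fires**

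The biopsy data are small: of the new subjects, "8 subjects provided their on-treatment biopsy". Up to 10 earlier subjects (Protocol 10.3) give at most 8 + 10 = 18. The search covers four dose measures, each linear and quadratic. With two biopsies per subject, one endpoint, selection on BIC alone and no dose-response at all, a dose model wins in 69–75% (8 subjects), 49–58% (12) and 31–40% (18). One pre-chosen linear measure wins in 10–30%. If the effect is proportional to dose, a dose model wins in 69–92%.

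**The case against.** - **Coding.** Setting dose to 0 at follow-up fits 7.4.2.1 poorly, because its measures stop at weaning; carrying the pre-weaning dose forward fits better. This stands, and it protects follow-up versus end of therapy. The contrast with baseline still falls to about 0.3 to 0.4 under a proportional effect.
- **Harmless codings exist.** One value per subject, or centring within each time-point, leaves the contrasts alone. True, but the SAP chooses neither.
- **6-month contrasts.** SAP section 10 defines experimental time without the 6-month visit, so the planned tables do not call for them. This stands as to the tables; 7.4.2.4 still plans the comparisons.
- **Unadjusted summaries remain.** SAP 7.4 requires every endpoint to be summarised over time, so a reader could notice a discrepancy. Those summaries are descriptive and do not replace an inferential result.
- **Trigger rates are soft.** The SAP also uses residuals and does not say how many of the eight primary endpoints must improve. Eight subjects is cohort 3 alone, whereas the main analysis combines cohorts 2 and 3. All of this stands: the percentages show that the rule can fire easily, not how often it will.
- **Reach is limited.** The rule is conditional and touches secondary endpoints only. The primary biopsy model and the 10 outcomes of 7.4.2.5 have dose-free models.

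**Conclusion.** The concern holds. Dose may be added to the models that define the hPTH effect, with no coding fixed and no dose-free fit retained. Seven outcomes and all 6-month contrasts have no other model. With visit-level dose, an assumed true change of 1.0 could appear as anything from about 0 to well above 1, or as 1.0 with a standard error roughly two to three times as large; under other codings nothing changes. The sizes rest on assumed dose distributions, SDs and effect shapes. The structural point follows from the SAP text and the algebra alone. This should be fixed, though it does not threaten the primary analysis. Confidence is medium, because the harm depends on the rule firing and on the coding then chosen.

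**What to change.** Delete the sentence in SAP 7.4.2.4 that adds dose to the non-biopsy models. State that all non-biopsy time contrasts come from the model without dose, and that this is the reported estimate where 7.4.2.4 and 7.4.2.5 overlap. If a dose analysis of these endpoints is wanted, present it separately as an exploratory dose-response description among on-treatment visits, with the measure and its coding defined and a statement that it does not estimate the treatment effect. Sections 7.4.2.1 and 7.4.2.2 need no change on this account. The cost is SAP wording only: no new data, and fewer models to fit.
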